4. CHANGES IN THE PLANNED ANALYSIS OF THE STUDY

[figure not shown]
This section includes changes and clarifications in the planned analysis presented in the study protocol.

Number	Date	Section of SEAP	Update	Reason
1	16 Jan 2017	5.1	The time window used in the definition of COPD, asthma, and other respiratory diagnosis has been extended to include 30 days after index date	To take into account differences in recording practices and potential delay in data recording in each data source, e.g., the general practitioner may have recorded the COPD diagnosis a few days after hospital discharge
2	16 Jan 2017	5.1	Patients classified under potential off-label use (with no asthma and no COPD diagnosis) will be further characterised	To describe how many have “probable COPD” based on the use of medications and age, and how many have respiratory conditions other than COPD and asthma
3	16 Jan 2017	5.3	The definition of COPD severity has been modified	To update the algorithm and make it similar to current GOLD 2016 guidelines [P16-00121]
4	16 Jan 2017	5.3	COPD severity will be described among the patients with COPD aged 40 years or older and among patients with COPD aged 39 years or younger	Patients aged 40 years or older are the population most likely to have COPD; description by age groups will facilitate comparisons with published literature where patients with COPD are frequently selected if they are aged 40 or older

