5.1 MAIN OUTCOMES

The main outcome of the study is the prevalence of off-label prescribing among new users of olodaterol. As a secondary outcome, the prevalence of off-label prescribing among new users of indacaterol will be assessed.

According to age and the presence of a recorded diagnosis of COPD and/or asthma, new users of olodaterol and new users of indacaterol will be classified into the following categories ([Table 4](#)):

- On-label prescribing: adults (aged ≥ 18 years at the index date) with a recorded diagnosis of COPD, with or without asthma
- Off-label prescribing:
 - Adults (aged ≥ 18 years at the index date) with a recorded diagnosis of asthma and without a recorded diagnosis of COPD, and
 - All children (aged < 18 years), irrespective of whether they have a recorded diagnosis of COPD (unlikely), asthma, or other respiratory disease
- Potential off-label prescribing: adults (aged ≥ 18 years) without a recorded diagnosis of COPD or asthma:
 - To further characterise these patients, recorded diagnosis of “other respiratory comorbidities” among these patients will be described (see conditions included in [Section 5.3.4](#)). The possibility of these patients having “probable COPD” will also be

Proprietary confidential information © 2017 Boehringer Ingelheim International GmbH or one or more of its affiliated companies

explored. Probable COPD will be defined by the presence of at least two prescriptions of long-acting beta2-agonist (LABA), long-acting muscarinic antagonist (LAMA), or inhaled glucocorticosteroid (ICS) (or combination) after the age of 40 years but not before (see lists of medications in [Annex Table 1-6](#)).

Table 4 Classification of patients according to age and indication of olodaterol and indacaterol

Recorded diagnosis ¹	Age	On-label prescribing: indication of COPD	Off-label prescribing	Potential off-label prescribing
COPD	≥18	Yes		
COPD and asthma	≥18	Yes		
Children, irrespective of any recorded diagnosis	<18		Yes	
Asthma (no COPD)	≥18		Yes	
No COPD, no asthma ²	≥18			Yes

COPD = Chronic Obstructive Pulmonary Disease.

- 1 Diagnosis recorded at any time before or on the index date and up to 30 days after the index date.
- 2 To further characterise adult patients with no COPD and no asthma, “potential COPD” and “other respiratory conditions” will be described among these patients.

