A random sample, stratified by age (18-39 years, ≥ 40 years) and sex, of up to 100 patient profiles from new users of each medication before and up to 30 days after the first exposure to the respective drug will be reviewed to confirm that the algorithms and codes developed to identify COPD and asthma are correct, i.e., that no codes have been missed and that the time window proposed is appropriate for the specific data source. The 100 olodaterol and 100 indacaterol new users will be randomly selected among the following groups by sex and age: 25 females aged 18-39 years, 25 males aged 18-39, 25 females aged ≥ 40 years, and 25 males aged ≥ 40 years; if there are less than 25 patients in the younger age groups, the remaining patient profile reviews, up to 25, will be done in the older age groups). Patient profiles are chronological listings of the routinely recorded codes that represent clinical events recorded in the study databases for individual patients. These listings include general practitioner diagnoses (if available, depending on the data source), outpatient and hospital discharge diagnoses and procedures, and dispensings of medications. The clinical review of patient profiles will provide more accurate information for evaluation of the indication and potential off-label use of olodaterol and indacaterol than use of codes alone. This information will be useful for developing clinical algorithms that can be applied to the evaluation of all new users of olodaterol and indacaterol. Patient profile review will be performed after the initial application of the electronic algorithm; if needed, the algorithms will be modified. The algorithm developed after patient profile review will be used for all the analyses to be performed for the interim and final study reports.

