7.5.2 Patient profile review to evaluate COPD and asthma algorithms

A description of the patient profile review process is presented in Section [5.1](#). Patient profiles will be created on a random sample, stratified by age (18-39 years, ≥ 40 years) and sex, of 100 new users of each study drug olodaterol and indacaterol. Results of the manual review of the patient profiles will be described and compared with the treatment indications identified through the electronic algorithms based on medical codes. These results will be described in the study report. Results reporting COPD, asthma, and “no COPD no asthma” as identified by the electronic algorithm and after patient profile review will be presented (Shell Table 11).

Proprietary confidential information © 2017 Boehringer Ingelheim International GmbH or one or more of its affiliated companies

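### The profile review cannot show whether 30 days is long enough, and sampling by age and sex alone leaves the number of non-COPD profiles to chance

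*SAP*

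**What the plan says.** SAP section 5.1 classifies new users by recorded diagnoses. The note to Table 4 sets the window: "Diagnosis recorded at any time before or on the index date and up to 30 days after the index date". Section 4 explains why the 30 days were added: "To take into account differences in recording practices and potential delay in data recording in each data source".

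The same section 5.1 plans a clinical review of a sample capped at 100 per drug. The material reviewed is described as "patient profiles from new users of each medication before and up to 30 days after the first exposure to the respective drug". Its stated aim is to check that the COPD and asthma algorithms and codes are correct, namely "that no codes have been missed and that the time window proposed is appropriate for the specific data source".

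The sample for each drug is "25 females aged 18-39 years, 25 males aged 18-39, 25 females aged ≥ 40 years, and 25 males aged ≥ 40 years". Unfilled places in the younger cells pass to the older ones. The review takes place after the algorithm has first been run, and the algorithm is changed if needed. Then: "The algorithm developed after patient profile review will be used for all the analyses to be performed for the interim and final study reports".

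Section 7.5.2 repeats the age and sex strata. It says that COPD, asthma and neither, "as identified by the electronic algorithm and after patient profile review will be presented", in Shell Table 11. Neither section sets a precision target, a minimum number of profiles per algorithm class, or a full-cohort result under the algorithm as it stood before the review.

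**The concern.** The review has two stated jobs, and for each the design leaves a gap.

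**Window.** If diagnoses are entered late, the natural question is how many first appear after the window closes. Profiles that close on the same day as the window cannot answer it.

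**Missed codes.** A missed COPD code moves a patient from off-label or potential off-label to on-label only if the algorithm had classed that patient as non-COPD. How many such patients are reviewed is not controlled.

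The review can change the definition behind the main outcome, the prevalence of off-label prescribing. SAP section 7.3 itself says that reliance on hospital diagnoses can overstate potential off-label use, and SAP Table 2 shows no general practitioner diagnoses for Denmark. A clean review that saw few informative profiles would give false comfort. If the algorithm is changed, no planned result shows how far the change moved the full-cohort prevalence.

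**Working it through.** **1. The window: the passages side by side**

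| Item | Last day covered | Source |
|---|---|---|
| Algorithm | index + 30 days | SAP 5.1, Table 4 note and text before Table 5 |
| Reviewed profile | first exposure + 30 days | SAP 5.1, profile review |
| Reason for the extension | delayed recording | SAP section 4, change 1 |

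The index date is the first recorded dispensing or prescription, so the two limits coincide. A first COPD code on day 31 or later appears in neither. Codes on days 0 to 30 are visible, so the review can show whether they occur, whether they cluster early, and whether a shorter window would give the same classes. Only the upper end is out of reach.

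**2. The plan's own figure**

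Four cells of 25 give 4 × 25 = 100 profiles per drug, as stated. I take this as 100 per drug within a data source, which SAP 5.1 does not say outright. If the 100 are shared across three sources, every count below shrinks.

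**3. Expected number of non-COPD profiles**

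The documents give no on-label share, so these shares are assumptions. Let q_y and q_o be the non-COPD share at ages 18-39 and 40 or older.

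Expected count = n_y × q_y + (100 − n_y) × q_o, where n_y is the number of profiles aged 18-39.

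- Younger cells empty (n_y = 0), q_o from 5% to 40%: 100 × 0.05 = 5, up to 100 × 0.40 = 40.
- Younger cells full (n_y = 50), q_y from 50% to 80%, q_o from 5% to 40%: 50 × 0.50 + 50 × 0.05 = 27.5, up to 50 × 0.80 + 50 × 0.40 = 60.

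**4. Chance of seeing at least one miss**

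Let m be the share of non-COPD patients with a missed COPD code (assumed 5%) and q the overall non-COPD share of the sample. Then P = 1 − (1 − q × m)^100.

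| Scenario | Expected non-COPD profiles | q × m | P |
|---|---|---|---|
| Younger cells empty, low | 5 | 0.0025 | 22.1% |
| Younger cells empty, high | 40 | 0.0200 | 86.7% |
| Younger cells full, low | 27.5 | 0.01375 | 75.0% |
| Younger cells full, high | 60 | 0.0300 | 95.2% |

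**5. With a fixed number n of non-COPD profiles**

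P = 1 − 0.95^n, and the one-sided 95% upper bound on m when none is found is 1 − 0.05^(1/n).

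- n = 50: P = 92.3%, bound 5.8%.
- n = 60: P = 95.4%, bound 4.9%.

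**The case against.** The strongest reply is that the review does more than this point credits.

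- **Window.** The SAP asks whether the window is appropriate, not only whether it is long enough, and its own example of delay is a few days after discharge. This stands. A reader might infer that the window cannot be tested at all, but days 0 to 30 are visible. What remains open is the upper end.
- **Number of profiles.** A reader might infer that very few profiles can be informative. The documents do not support that. Half the sample is assigned to ages 18-39, and the SAP considers COPD most likely at 40 or older. If those cells fill, 28 to 60 non-COPD profiles are plausible. The missing general practitioner diagnoses in Denmark could raise the share there.
- **Two drugs, one code list.** COPD codes are not drug-specific, so the two samples can be read together. In the least favourable case this gives 1 − (1 − 0.0025)^200 = 39.4% instead of 22.1%. That helps, but the number is still not controlled.
- **COPD-coded profiles matter too.** An unlisted code can sit beside a listed one, and only these profiles reveal false COPD codes. ICPC R78 appears under chronic bronchitis in SAP Table 5 and under acute bronchitis in SAP Table 9. This stands, and it argues against shifting the sample too far. Protocol section 9.3.2.3 also gives a reason for the age and sex strata: predictive values are expected to vary with COPD prevalence.
- **Other checks.** A reader might infer that the review is the sole safeguard for the main outcome. It is not: SAP sections 5.1 and 7.5.1 describe probable COPD and other respiratory conditions among adults with neither diagnosis. That description does not test for unlisted codes or late recording.
- **Unseen material.** SAP section 7 places the table shells in a separate file, and section 9.2, cited for database-specific rules, is not in the text available. How Shell Table 11 handles the unequal sampling therefore cannot be judged.

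**Conclusion.** The point holds in a limited form. The window part follows from the text alone: the review cannot show whether 30 days is long enough, which is the question the SAP's own reason raises. The sampling part is a lack of assurance, not a demonstrated shortage. Under assumed non-COPD shares (5-40% at 40 or older, 50-80% at 18-39) and an assumed 5% miss rate, the chance of seeing a class-changing miss could be about 22% or about 95%, and the plan does nothing to settle which. No single detection figure should be quoted, because the documents give neither share. The main outcome is not shown to be wrong. What is missing is evidence that its definition was adequately checked, and a way to see how far the review changed the result.

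**What to change.** 1. For the sampled patients only, list records beyond day 30, for example to 180 days where available. The length is a design choice that the documents do not supply. Tabulate the day of the first COPD code. Leave the outcome definition at 30 days.
2. Keep about 100 profiles per drug and the age and sex balance, but set a minimum number of non-COPD profiles, for example 50. Keep enough COPD-coded profiles to check for false COPD codes. This is feasible because the algorithm has already been run when the sample is drawn. State whether the numbers apply per data source.
3. Report the main outcome for the full cohort under both the pre-review and the post-review algorithm.

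**Cost.** The number of reviews is unchanged. The additions are SAP wording, a longer extract for the sampled patients and one more column of results. Later records will be incomplete for recent initiators: with data to the end of 2015 for the interim report in PHARMO and Denmark (SAP Table 1), only patients starting by about early July 2015 have 180 days. Some late codes may be new disease, so the tabulation informs judgement on the window and does not by itself justify extending it. If a sample would otherwise hold fewer than 50 non-COPD profiles, the check on COPD-coded profiles becomes somewhat less precise.

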5.3 OTHER VARIABLES

New users of olodaterol and indacaterol at the index date will be characterised according to demographic characteristics, available data on lifestyle habits, health care resource utilisation, comorbidities, and use of medications. Patients with a prior diagnosis of COPD will also be characterised based on their COPD severity.

For conditions and medications, if information on a particular binary covariate is available in the data, patients will be assumed to have the factor only if there is evidence for its presence (i.e., absence of any records with a diagnosis code for a condition will be taken to mean absence of the condition). The only exception to this principle will be when “missing” (or

Proprietary confidential information © 2017 Boehringer Ingelheim International GmbH or one or more of its affiliated companies

other value, e.g., “unknown”) is one of the possible values recorded for the variable in the data source, in which case the value as reported within the data source will be retained in the analysis as one of the possible values.

5.3.1 Demographic and lifestyle habits at the index date

The following demographic and lifestyle variables, as available in each data source, will be considered at the closest measure before and including the index date. Depending on the data source and the demographic or lifestyle variable, information may be restricted to a specific period before the index date (e.g., 1 year). The categories for these variables will depend on data source availability and will be described in the study report. The proposed categories and data availability by data source are presented in [Table 6](#). Additional details on database-specific specifications for the definition of these variables in each data source are described in [Section 9.2](#).

Table 6 Demographic and lifestyle variables: proposed definition, units, and categories, by data source

Variable	Definition, units, and categories	PHARMO, the Netherlands	National Registers, Denmark	IMS RWE LPD, France
Age	Years: year of the index date minus year of birth as a continuous variable and as a categorical variable of the following age groups: < 18, 18-29, 30-39, 40-49, 50-59, 60-69, 70-79, and 80+ years			
Sex	Male, female			
Smoking status	Depending on data source and data availability	Ever use of smoking cessation medication (yes/no), and smoking status (current, former, never, and missing) in PHARMO-GP	N.A.	Smoker/non-smoker
Alcohol consumption	Yes/No	Alcohol-related disorder	Alcohol-related disorder	Alcohol-related disorder
Body mass index (kg/m ²)/obesity	Underweight (< 20), normal (20 to < 25), overweight (25 to < 30), obese (≥ 30), and missing	BMI and diagnosis of obesity or overweight	Diagnosis of obesity or overweight	BMI and categories
Socioeconomic status indicators or proxies	Depending on data source	Based on postal code	N.A.	Geographical location of physician
Duration of enrolment prior to index date	In years and defined as the year of the index date minus year of enrolment. Does not include the 30 days after the index date or the duration of follow-up after the index date			

BMI = Body Mass Index; N.A. = Not Available.

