| Data Element   | PHARMO (Netherlands)  | National Registers, Denmark                             | National Registers, Sweden                              |
|--|---|---|---|
| Lifestyle risk factors (smoking status, BMI, alcohol intake) | Yes, if recorded by GPs   | Yes, if recorded by GPs                                 | Yes, if recorded by GPs                                 |
| Data availability  | Annual  | Since 1994  | Since 2005  |
| Updates  | Pharmacy data: 2 months
All other data: annual; available following Q3-Q4  | Annual  | Annual  |
| Approximate time lag   | No  | 1 year  | 2012 data will be available in 3Q-4Q 2013               |
| Data transfer  | Review by the independent compliance committee STIZON/ PHARMO Institute
This committee consists of representatives of the individual data suppliers and is chaired by a privacy expert | No, requires collaboration with local investigator      | No, requires collaboration with local investigator      |
| Approval process   | Data application and ethics committee approval required   | Data application and ethics committee approval required | Data application and ethics committee approval required |

ATC = Anatomical Therapeutic Chemical; BMI = Body Mass Index; GP = General Practitioner; ICD-9-CM = *International Classification of Diseases, 9th Revision, Clinical Modification*; ICD-10 = *International Statistical Classification of Diseases and Related Health Problems, 10th Revision*; ICD-10-CM = *International Classification of Diseases, 10th Revision, Clinical Modification*; ICPC = *International Classification of Primary Care*; NCSP = *Nordic Medico-Statistical Committee's Classification of Surgical Procedures*.

1 Eurostat. 2013. Available at: website: [epp.eurostat.ec.europa.eu/tgm/table.do?tab=table&init=1&language=en&pcode=tps00001&plugin=1](http://epp.eurostat.ec.europa.eu/tgm/table.do?tab=table&init=1&language=en&pcode=tps00001&plugin=1). Accessed January 28, 2014.

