6.5 HANDLING OF MISSING DATA AND OUTLIERS

The extent of missing data will be evaluated and described. Due to the nature of this study, no imputation of missing data is planned. Missing values are expected in some sociodemographic variables depending on the definition used and in variables related to exposure characterisations such as strength or daily dose. Degree of missingness will depend on the database, and some data sources will have variables that are not available, such as oxygen therapy in PHARMO and hospitalisations in IMS RWE LPD. Diagnoses, prescriptions, and dispensings can be identified in the databases only if they are recorded. Thus, all patients with a certain diagnosis/dispensing in the database will be coded as having

Proprietary confidential information © 2017 Boehringer Ingelheim International GmbH or one or more of its affiliated companies

the respective condition/exposure to the respective drug. All others will be coded as not having the disease/not being exposed to the drug. Therefore, uncoded diagnoses/dispensings may result in misclassification and not in missing values.

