ANNEX 1. CODES FOR COMORBIDITIES AND OTHER COMEDICATIONS

Annex Table 1-1 ICD-10 codes for alcohol-related disorders

ICD-10 codes	Description
85.9 in ICD-10, and I85.00 in ICD-10-CM	Oesophageal varices without mention of bleeding
E24.4	Alcohol induced pseudo-Cushing's syndrome
F10.1-F10.9	Alcohol dependence syndrome/Mental and behavioural disorders due to use of alcohol: dependence syndrome
G31.2	Degeneration of nervous system due to alcohol
G62.1	Alcoholic polyneuropathy
G72.1	Alcoholic myopathy
I42.6	Alcoholic cardiomyopathy
I85.0 in ICD-10 and I85.01 in ICD-10 CM	Oesophageal varices with bleeding
I85.0 in ICD-10-CM	Oesophageal varices in diseases classified elsewhere/Secondary oesophageal varices with bleeding
K29.2	Alcoholic gastritis
K29.20	Alcoholic gastritis without mention of haemorrhage/Alcoholic gastritis
K29.21	Alcoholic gastritis with haemorrhage/Alcoholic gastritis
K70.x	Alcoholic liver disease
K85.2	Alcohol induced acute pancreatitis
K86.0	Alcohol induced chronic pancreatitis
Z50.2	Alcohol rehabilitation
Z71.4	Alcohol abuse counselling and surveillance
Z72.1	Alcohol use

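### SAP Table 6 fills 'Alcohol consumption, Yes/No' from an alcohol-related-disorder code list and reads no code as 'No', so drinkers without a listed code are reported as non-consumers

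*SAP*

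**What the plan says.** The protocol lists alcohol consumption among the lifestyle variables (Section 9.3.3.1). It plans to show new users by category of consumption, as far as each database allows (Section 9.7.4). Its database overview (Section 9.4.4, Table 8) has the entry "Lifestyle risk factors (smoking status, BMI, alcohol intake) | Yes, if recorded by GPs" for PHARMO and says the same for Denmark and Sweden.

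SAP Table 6 keeps the protocol's variable name but defines the row as "Alcohol consumption Yes/No Alcohol-related disorder". That is the only entry for each of the three sources: PHARMO, Denmark and France.

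For binary covariates, SAP Section 5.3 states that "absence of any records with a diagnosis code for a condition will be taken to mean absence of the condition". The one exception is a source that itself records a value such as missing or unknown, "in which case the value as reported within the data source will be retained in the analysis as one of the possible values". SAP Section 6.5 repeats the rule and accepts that "uncoded diagnoses/dispensings may result in misclassification and not in missing values".

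The ICD-10 codes are in SAP Annex Table 1-1. Three of its 18 rows are "Oesophageal varices without mention of bleeding", "Oesophageal varices with bleeding" and "Oesophageal varices in diseases classified elsewhere/Secondary oesophageal varices with bleeding". The ICPC list in Annex Table 1-2 has two codes, for chronic and acute alcohol abuse.

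**The concern.** The label names a behaviour and the content is a disease proxy. Alcohol is the only row of Table 6 that keeps a behaviour name over a diagnosis in every source, with no way to show that consumption is unknown. Its neighbours are handled differently. Smoking is marked not available in Denmark and has a missing level in PHARMO-GP. The body mass index row has obesity in its name and a missing level among its categories.

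Describing the baseline characteristics of new olodaterol users is the second primary objective, and the indacaterol description is its secondary counterpart. SAP Section 7.1.1 reports lifestyle characteristics for each drug in three populations: all new users, adults, and patients aged 40 or older with COPD. A row that states the wrong thing would therefore recur in each of these tables, in each source. Someone reading the report tables without Table 6 at hand would take 'No' to mean that the patient does not drink.

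**Working it through.** The documents state no prevalence, sensitivity or predictive value for this variable, so there is no plan figure to reproduce. The check is to follow the definition for particular patients, and then to ask whether a size can be given.

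**Step 1: follow the rule.**

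| Patient | Listed code? | Reported 'Alcohol consumption' |
|---|---|---|
| Drinks, has a listed code | Yes | Yes (correct) |
| Drinks, no listed code | No | No (wrong) |
| Does not drink, varices of another cause | Yes, through a varices row | Yes (wrong) |
| Does not drink, no listed code | No | No (correct) |

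The second line follows from Table 6 together with the absence rule. The third follows from Annex Table 1-1: the three varices rows are the only ones of the 18 whose descriptions do not mention alcohol.

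**Step 2: direction.** Let p be the true share of drinkers, d the share of patients with any listed code, and f the share of coded patients who do not drink. The table reports 'Yes' for d, while the truth is p. The two errors pull in opposite directions, and the net error is under-reporting by p − d whenever fewer patients carry a code than drink. That is to be expected of a list made up mainly of disorders, but neither p nor d is in the documents.

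**Step 3: can it be sized?** The share of drinkers reported as 'No' is

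1 − d(1 − f)/p.

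All inputs below are assumptions, with f from 0 to 10% throughout.

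| p | d | Drinkers reported as 'No' |
|---|---|---|
| 50% to 90% | 1% to 5% | 90% to 99% |
| 50% to 90% | 10% | 80% to 90% |
| 30% | 10% | 67% to 70% |
| 30% | 20% | 33% to 40% |

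Example: p = 70%, d = 3%, f = 10% gives 1 − 0.03 × 0.90/0.70 = 0.961. At the other end, p = 30%, d = 20%, f = 0 gives 1 − 0.20/0.30 = 0.333. The result runs from about one third to almost all, depending on inputs that the plan does not contain.

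**Step 4: where could recorded intake be used instead?** Protocol Table 8 names PHARMO, Denmark and Sweden, in each case only if the GP recorded it. In the SAP, Sweden is no longer a source, Denmark has no GP data (SAP Table 2), and the French database is not covered by protocol Table 8. That leaves the PHARMO-GP subset.

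**Step 5: what depends on the row?** Alcohol does not enter the on-label and off-label classification (SAP Sections 5.1 and 7.5.1) or COPD severity (Section 5.3.3). Confounding adjustment is marked not applicable (Section 7.4).

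**The case against.** The best defence is that the proxy is open. Each source cell says alcohol-related disorder, and the annex titles say the same. The absence rule is usual for diagnosis-code variables, and Section 6.5 admits the misclassification it causes. Table 6 calls its categories proposed and leaves source-specific detail to Section 9.2, which is not in the text available here and may refine the definition. The protocol warned that lifestyle data might be partly or wholly unavailable (Section 9.3.3). Much of this stands, and it keeps the point minor. It does not repair the label: disclosure in the SAP does not change what a results table headed 'Alcohol consumption: No' tells its reader.

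Three stronger readings are tempting, and the documents do not carry them.

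- A reader might infer that the variable rests on disorder codes alone. For ICD-10 that is not quite so: Annex Table 1-1 also has Z72.1 (alcohol use), Z71.4 (counselling) and Z50.2 (rehabilitation). It is true only of the ICPC list.
- A reader might infer that nearly every drinker will be shown as a non-consumer. That holds only if listed codes are rare relative to drinking, which the documents do not quantify.
- A reader might infer that available intake data are being ignored. Availability is conditional on GP recording and, among the SAP's sources, documented only for PHARMO-GP. Table 6 is the later statement for that subset and lists smoking status but no intake, which fits intake not being usable. Section 9.2 might also cover it.

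The first varices code is printed as 85.9, without its letter. The same cell gives I85.00 for the other coding system, so this may be a typing or text-extraction slip. It needs a check and supports no conclusion.

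**Conclusion.** The point holds as a mismatch between label and content. Followed as written, the row reports drinkers without a listed code as 'No', and the varices rows can add non-drinkers to 'Yes'. The expected net direction is under-reporting of consumption, on the assumption that fewer patients carry a listed code than drink. No size can be given from the documents; the percentages in the working are illustrations from assumed inputs. The consequence is limited to one descriptive baseline row for each drug. Off-label prevalence is untouched. This is a minor correction, worth making because it is nearly free.

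**What to change.** 1. In Table 6 and the matching table shells, rename the row 'Recorded alcohol-related disorder (yes / none recorded)' for all three sources.
2. Remove the three oesophageal varices rows from Annex Table 1-1. Counting them only in patients who also have an alcohol-specific code would give the same yes/no result, since such a patient is already a 'yes', so removal is simpler.
3. Ask the PHARMO partner whether GP-recorded alcohol intake can be extracted. If it can, report it in PHARMO-GP as a separate 'Alcohol consumption' row with a 'missing' level. If it cannot, say in the report that consumption is not available.
4. Check the printed code 85.9 against the source list.

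Items 1, 2 and 4 cost only SAP and shell wording and an edit to one code list. Item 3 costs a query and, if the answer is yes, an added variable in one extraction. Its effort is not known from the documents, and intake may be missing for many patients, which the added level would show.

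Section 9.2 should be brought into line with whatever is chosen.
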